#### 1. Background and Significance

Homonymous visual field loss (HVFL) affects the same side (left or right) of the visual field in each eye. HVFL results from post-chiasmal damage to the visual pathways and is contralateral to the side of the brain injury. The most common cause is stroke followed by traumatic brain injury, tumors, and brain surgery. In the United States, people with homonymous hemianopia (the loss of one half of the visual field) are permitted to drive in states where they meet the visual requirements for either a regular or a restricted license. For instance, they can drive in New Hampshire, Colorado and California where there are no minimum field requirements. People with homonymous quadrantanopia (the loss of one quarter of the visual field) are permitted to drive in most states because their field loss only affects one quadrant rather than a complete hemifield (as in hemianopia).

Drivers with HVFL could compensate for their vision loss by scanning toward the blind side of the visual field using eye and head movements. However, prior research suggests that drivers with HVFL sometimes fail to scan to the blind side when approaching an intersection or do not scan far enough resulting in impaired responses to hazards. A large gaze scan, up to 90°, composed of head as well as eye movements, may be needed to see hazards approaching from the blind side at a four-way intersection. People with HVFL do not have any stimuli from peripheral vision as to when to scan to the blind side (because they do not have any peripheral vision on that side). Therefore, they may be unaware that they have failed to scan to the blind side unless there is some consequence (e.g., a near crash, or another driver honks at them)

In a prior proof-of-concept driving simulator study, we evaluated auditory reminder cues as a method to alert individuals with HVFL when they failed to make a large scan to the blind side on approach to an intersection. We found that the reminder cues promoted a more proactive style of scanning, i.e., participants were more likely to make an early large scan in drives with than without the reminders, and participants who scanned less well showed greater improvement than participants who scanned well without the reminders. Moreover, when participants made an early large blind side scan, response times were significantly faster than when they did not make an early scan. These results

suggest that reminder cues might be a useful tool in training aimed at improving scanning of drivers with HVFL at intersections.

## 2. Specific Aims and Objectives

Based on the positive findings from our proof-of-concept study, the goal of this pilot clinical trial is to evaluate short-term effects of reminder cue training for drivers with HVFL as the basis for a future controlled clinical trial with long-term follow up. We will test the hypothesis that in the short term (1 to 2 weeks) the training improves scanning on approach to intersections.

## 3. General Description of Study Design

This is an open-label, single-arm, pilot clinical trial to evaluate the efficacy of reminder cue scanning training for people with HVFL. There will be a driving simulator evaluation before and after training to quantify changes in scanning following training.

## 4. Subject Selection

### Inclusion criteria:

- HVFL (homonymous hemianopia or homonymous quadrantanopia) for at least 3 months to avoid the confound of spontaneous recovery (most likely to occur within 3 months of the onset of the field loss).
- Binocular visual acuity of at least 20/40
- Prior (or current) driving experience
- At least 16 years of age (there will be no upper age limit)
- Able to attend multiple study visits at Schepens
- English speaking (sufficient to participate in study procedures)

### Exclusion criteria:

- Physical or general health problems that could impair the ability to operate the controls of the driving simulator.

### Recruitment sources and procedures:

A trained member of the study team will handle recruitment. Depending on the recruitment source, the study team member will either contact the potential participant or the potential participant will contact the study team member.

Recruitment sources include:

1. RPDR: Research Patient Data Registry

We will use the RPDR database to screen subjects who have not opted out of receiving information about suitable studies. We will query the database to include patients with an ICD

code of Homonymous Visual Field loss who are alive and do not have ICD codes of other physical or cognitive disabilities listed, and do not have interpreter services mentioned on the list. We will begin by contacting 100 subjects in chronological order from most recent to older encounter dates. The research assistant or postdoc on the study team will use the RPDR database to query this data. [name] will be the workgroup leader and approve these requests to receive mailing information of potential subjects to contact. Personalized letters will either be mailed out to these potential subjects or sent via Patient Gateway. (RPDR recruitment letter attached). Persons responding with interest in learning about the study can contact the research assistant or study coordinator on the phone who will then use the telephone script (attached) to explain the study to the participant. The PI will conduct ongoing monitoring of patient responses to ensure that the selection criteria are identifying the right patients and will submit complaints about this method of recruitment to the IRB as an “other” event.

2. MGB Rally

The project will be advertised on the Rally online platform of Mass General Brigham where the study information will be provided, and anyone can show interest in participation. The potential subjects will be contacted using the telephone script, and/or email attached (depending on the preference they indicate when responding on the Rally website). The preview of the Rally advertisement will be submitted after the protocol is assigned a number.

3. Recruitment from clinics at MEE

Participants will be recruited from neuro-ophthalmology clinics and the vision rehabilitation clinic at MEE. We will send practitioners a letter requesting their help with recruitment along with a recruitment pack. The pack includes a flyer, an information sheet about the study (for the practitioner to give to patients who might be interested), and a permission-to-be-contacted form. Potential participants can express their interest in one of three ways: 1) By contacting the study coordinator directly using the contact information on the sheet, 2) By indicating their interest via a QR code which links to a REDCap survey where they can enter their basic eligibility information (such as whether they are licensed to drive and whether they have normal vision) and contact information (see uploaded preview of REDCap questionnaire), or 3) By completing the permission-to-be-contacted form, which will be returned to Schepens by the healthcare provider. Potential participants will be contacted using the telephone script and/or email, based on their preference indicated in the REDCap survey or the permission-to-be-contacted form.

4. Recruitment from other clinics in the Greater Boston area

We will also recruit participants from other ophthalmology and optometry clinics in the Greater Boston area. The procedures will be the same as for recruitment from clinics at MEE.

**How recruitment goals match the prevalence rates of the condition/disease being studied and the populations most impacted by the condition/disease being studied?**

HVFL affects both genders and members of all racial and ethnic groups. Therefore, during this study, no individuals will be excluded based on race, ethnicity or gender, and every attempt will be made to ensure that minorities and women meeting the eligibility criteria are recruited for participation. It is expected that approximately equal numbers of males and females will be recruited. There are some racial/ethnic group differences in the prevalence of certain diseases (e.g., stroke) that cause HVFL and we expect that this will be reflected in the sample populations that we recruit.

## **Methods to enhance enrollment of diverse individuals and under-represented populations**

We are not proposing any specific outreach programs for recruiting specific gender, racial and ethnic groups, as all eligible participants will be recruited regardless of gender, race and ethnicity.

## **5. Subject Enrollment**

### **Pre-screening**

During the telephone call when potential participants are informed about the study they will be asked if they have homonymous visual field loss (hemianopia or quadrantanopia) and whether they have driving experience (prior or current) (see telephone recruitment script). If they respond no to one or both questions, they will be told that they do not meet the criteria for the study.

### **Consent process:**

Informed consent will be obtained at the start of the first visit. Consent procedures will be conducted in a quiet, private area at the study site by a trained member of the study team. At the start of the first visit, the purpose, risks, and procedures of the study will be explained. Subjects will be given ample opportunity to discuss all aspects of the study and ask questions before signing the form. The PI, [name], will be available to answer questions. If potential participants are unsure about whether they want to participate, they will be able to discuss the study with other people such as family, caregivers, or friends before deciding. They are not obligated to sign the form on the same day, and may take time to decide before signing. Participants will be told that they are under no obligation to do the study and that they can withdraw from the study at any time without consequence. If participants so request, consent forms will be read aloud to them. Participants will be provided with a copy of the consent form.

*The process for obtaining consent from non-English speakers if applicable*

N/A - Participants will need to speak sufficient English to be able to participate in study procedures. We do not have funds for interpreter services for this project; non-English speakers will not be recruited.

*The process to determine capacity to consent and use surrogate decision makers if applicable*

N/A – All participants will be capable of providing voluntary informed consent

*Procedures to minimize undue influence to enroll investigators' own patients*

N/A

*Post-consent intervention assignment and randomization method*

N/A

## **6. Study Procedures**

Typically, the study will involve 7 visits (Table 1) over a period of about 10 weeks. Each visit will be about 2 hours.

Visit 1: Screening and pre-training driving performance

At Visit 1, subjects will undergo vision screening to determine whether they meet the study criteria. Vision measures will include visual acuity (computerized chart) and visual field extent (Goldmann perimeter). In addition, contrast sensitivity may be measured (computerized chart). Participants will also be administered questions to document demographics, relevant ocular and driving history. Participants who meet the eligibility criteria will then complete a pre-training evaluation of driving performance in the driving simulator (see below). Normally the pre-training driving evaluation will be conducted at Visit 1, but, if necessary, a separate visit will be arranged (e.g., if the participant is fatigued).

Neglect status will be evaluated using clinical tests of neglect such as the Bells test and the Schenkenberg Line Bisection test. Both are pencil-and-paper tests: in the Bells Test, participants circle all the bells on the sheet, while in the Line Bisection Test, they mark the center of each line on the sheet. Cognitive status will be evaluated using the Montreal Cognitive Assessment Test (MoCA).

#### Visits 2 to 4: Scanning training in the driving simulator

At visits 2 to 4, subjects will receive reminder cue scanning training in the driving simulator. These visits will be scheduled within about a 3-week period (ideally one training visit per week). During training, participants will drive along pre-determined routes in the simulator while their head movements are tracked in real time using the remote camera-based tracking system in the simulator. They will receive a scanning reminder cue whenever they fail to make a large scan to the blind side before entering an intersection. The reminder cue will be in the form of an audio cue (a short “beep” from a loudspeaker on the blind side, as used in the preliminary study) or a tactile cue (e.g., vibrations from the car seat on which the subject is sitting).

#### Visit 5: Post-training driving performance

At visit 5, participants will complete a post-training evaluation of driving performance in the driving simulator within 2 weeks of finishing the training.

#### Visit 6: One-month post-training driving performance

To evaluate the short-term effects of the training, at visit 6, participants will complete a post-training evaluation of driving performance in the driving simulator approximately one month after Visit 5.

#### Visit 7: One-year post-training driving performance

About a year after Visit 6, they will return for a long-term post-training evaluation of driving performance in the driving simulator.

**Table 1: Schedule of visits and assessments**

	Visit 1	Visit 2	Visit 3	Visit 4	Visit 5	Visit 6	Visit 7
Informed Consent	X						
Visual acuity	X						
Visual fields	X						
Contrast sensitivity	X						
Neglect tests	X						
Cognitive status test	X						
Ocular, driving and other relevant history	X						
Driving performance evaluation	X				X	X	X
Reminder cue training		X	X	X			

Driving simulator

The simulator (at Schepens Eye Research Institute) comprises multiple screens, an adjustable driver's seat, steering wheel, accelerator, and brake pedals. Participants will drive along predetermined routes in the virtual world guided by audio cues simulating GPS navigation. There will be other traffic on the road and the routes will include a variety of maneuvers in a city environment. Hazards (such as pedestrians and other vehicles) will be programmed to appear in various situations in some of the drives.

Participants will be instructed to obey all normal rules of the road, avoiding collisions, and maintaining a speed near the posted speed limit.

After acclimatization and practice drives in the driving simulator, each participant will complete evaluation drives (about 10 minutes each) at Visits 1 and 5- 7 without scanning reminder cues and training drives (about 6 minutes each) with reminder cues at Visits 2-4. Head and eye movements of the driver will be recorded using a remote camera-based tracker mounted in the simulator. In addition, a video camera placed behind the participant will be used to record the screens of the driving simulator to facilitate interpretation of driving behavior data automatically recorded by the simulator. Rest breaks will be scheduled into testing sessions and subjects will be able to take a break or stop at any time, without consequence.

Plans for return of research results

There are no plans to return research results to subjects at the end of the study. If subjects indicate an interest in the outcome of the study, a note-to-file will be made, and the PI may share the final published manuscript with these study participants.

Primary and secondary outcomes

- **Primary outcome measure:** Our primary outcome measure will be the proportion of intersections at which participants make an early large scan to the blind side (side of the field loss) and the proportion of detected hazards approaching from the blind side, pre- versus post-training.
- **Secondary outcome measures:** The secondary outcomes will include additional measures of scanning behaviors (including the number, direction, and magnitudes of scans) and responses to hazards (such as time to fixate the hazard and time to respond).

#### Study termination criteria

Study participation will be terminated if:

- The subject no longer meets the inclusion criteria
- The subject experiences a serious adverse event

Remuneration Subjects will receive \$50 per study visit for study participation and travel expenses will be reimbursed to a maximum of \$50.

#### Masking

This is an open-label study so there will be no masking

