#### Planned safety monitoring

This is a minimal risk, single-site, pilot clinical trial. A data safety and monitoring board is not required. The PI will be responsible for safety monitoring, which will be performed as part of the outcomes monitoring.

Outcomes monitoring

Approximately once a quarter, data summaries will be reviewed by an internal committee comprising the PI and members of the research team at Schepens to monitor data quality, primary outcomes and study progress. Data summaries will be produced by the research assistant (including data on topics such as subject enrollment, withdrawals, primary outcome measures, and any safety issues).

Study stopping rules

There are no study stopping rules (other than the criteria for terminating a subject from the study, detailed in the section on study termination criteria above)

Internal monitoring of source data

The PI has overall responsible for monitoring the integrity of the data. The research assistant will be responsible for ensuring accuracy and completeness of data records and informed consents. Research staff will enter data into study spreadsheets in a timely fashion and all data will be checked by another researcher to ensure integrity. Summaries of data will be reviewed by the study team to further ensure integrity.

Independent monitoring of source data

The proposed research is no more than minimal risk. Independent monitoring of the source data is not required.

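### Open-label status is given as the reason for no masking at all, but drive recordings could still be scored without knowledge of visit

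*Combined protocol and SAP*

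**What the plan says.** All references are to the combined protocol and SAP.

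- **Section 6, Masking**, is one sentence: "This is an open-label study so there will be no masking". It makes no separate provision for those who process or score data.
- **Section 3**: "This is an open-label, single-arm, pilot clinical trial to evaluate the efficacy of reminder cue scanning training for people with HVFL".
- **Section 6 (outcomes) and section 9**: the primary outcome is a pair of proportions compared before and after training. One is the share of intersections with an early, large blind-side scan; the other is the share of blind-side hazards detected.
- **Section 6, Driving simulator**: a camera-based tracker records head and eye movements. Video of the simulator screens is kept "to facilitate interpretation of driving behavior data automatically recorded by the simulator". Evaluation drives at Visits 1 and 5 to 7 carry no reminder cues.
- **Section 10, Outcomes monitoring**: "Approximately once a quarter, data summaries will be reviewed by an internal committee comprising the PI and members of the research team", and the purpose is "to monitor data quality, primary outcomes and study progress". The research assistant prepares the summaries, and primary outcome measures are among their listed contents.
- **Section 10, Internal monitoring of source data**: "Research staff will enter data into study spreadsheets in a timely fashion and all data will be checked by another researcher". There is no data safety monitoring board, no independent source-data monitoring and no study-level stopping rule.

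**The concern.** Open label describes who knows what treatment is being given. Here participants and trainers must know. Whoever turns a tracker file into a yes or no for each intersection, or decides whether a hazard was detected, need not know whether the drive came before or after training.

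This matters more than usual because there is no control arm. Knowing the visit is knowing the treatment status, and the whole effect estimate is the difference between visits. If classification leaves any room for choice, and those choosing know the visit or have seen the pre/post difference so far, the choices can drift towards the expected answer. The trial is meant to supply data for a later randomized trial (section 9), so an inflated difference would carry into that trial's planning.

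**Working it through.** **1. The plan's own figure.** Section 9 gives 16 completers, Cohen's d of about 0.8, a paired t-test, α = 0.05 and about 80% power. Sidedness is not stated; two-sided is assumed here. Exact power uses the noncentral t with df = n − 1 and noncentrality d√n.

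- n = 16: df = 15, noncentrality 0.8 × √16 = 3.2, power 84.8%.
- n = 15: power 82.1%, the smallest n that reaches 80%.
- Power of 80% at n = 16 corresponds to d of about 0.75.

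The sample size is adequate for its stated inputs, and masked scoring would leave n, α and power unchanged. The point concerns bias, not a wrong number.

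**2. Does the stated reason support the rule?** Section 6 offers open-label status as the only ground for no masking. That covers participants and the staff who deliver training. It does not cover scoring of stored recordings, and no other section provides for masked scoring.

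**3. Is there room for choice in scoring?**

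- The outcome definitions in sections 6 and 9 give no time or distance that makes a scan early, no angle that makes it large, and no criterion for detection. Section 1 mentions gaze scans of up to 90° as what may be needed at a four-way intersection; it does not offer this as a scoring threshold.
- For training (section 6, Visits 2 to 4), head movements are tracked in real time. For evaluation, head and eye movements are both recorded. The protocol does not say which signal defines the outcome scan.
- Video is there to help interpret the automatic record, so some human interpretation is foreseen.

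**4. Who sees results while these choices are open?** Section 10 puts primary outcome measures before the PI and research-team members about every quarter. Data are entered by research staff and checked by another researcher. No one is named as scorer, and no scorer is described as separate from the team.

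**5. How large could the effect be?** The documents give nothing from which to estimate a scoring bias. To show scale only, assume no true effect and a systematic scoring shift of b standard deviations of the paired difference. The noncentrality is then b√16 = 4b, and the two-sided rejection rate at n = 16 is:

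| Assumed shift b (SD) | Noncentrality 4b | False-positive rate | b as a share of d = 0.8 |
|---|---|---|---|
| 0 | 0 | 5.0% | 0% |
| 0.1 | 0.4 | 6.6% | 12.5% |
| 0.2 | 0.8 | 11.7% | 25% |
| 0.3 | 1.2 | 20.3% | 37.5% |

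The shifts are assumptions, and the paired t-test stands in for the mixed models of section 9.

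**6. Is masking by visit feasible?** Evaluation drives have no cues at any visit, so cue presence would not reveal the visit. Files already carry subject codes (section 7, Confidentiality), and the video is taken from behind the seat without showing the face (section 7, Driving Simulator). The plan does not say whether the same routes are used at each evaluation. If routes differ by visit, masking would be only partial.

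**The case against.** The strongest reply is that most of the measurement is automatic. The simulator and tracker record the data. In training, a cue is triggered in real time when no large blind-side scan is made, so some working rule for a large scan presumably exists. An algorithm applied identically to every drive leaves little room for a scorer's expectations, and writing down the thresholds would remove much of the concern without masking. This largely stands, and it limits the severity. It does not close the point: the protocol neither states that rule nor says it will define the outcome, and it foresees interpretation with the help of video.

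Three stronger readings are tempting, and the documents do not support them.

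- *The quarterly looks inflate the false-positive rate.* If unadjusted paired t-tests were run and acted on, 200,000 simulated null trials give about 8.5% with looks at 8 and 16 participants, and about 13.5% with looks at 4, 8, 12 and 16. But section 10 describes summaries, not tests; section 9 sets a target of 16 completers; and there is no study stopping rule. Looks that are never acted on leave the rate at 5%. Those simulations model optional stopping, so they say nothing about choosing a scan threshold after seeing data.
- *The people who score are the people who review.* This is a reasonable inference from section 10, but the scorer is never named. Nor do the documents say that hazard detection is scored from video.
- *Unmasked scoring is the main bias.* This is not shown. Practice in the simulator, participant expectation and regression to the mean also affect a single-arm pre/post contrast, and masked scoring addresses none of them.

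It is also fair to say that the quarterly review is the only group review of safety and data quality described. In a minimal-risk pilot, withholding pre/post values from it is a secondary and more debatable request.

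**Conclusion.** The point holds in a limited form. The protocol excludes all masking for a reason that does not reach the processing of recordings. Undefined scoring terms, interpretation aided by video and team access to accumulating primary outcomes then leave a route by which processing choices could follow the result. This is an avoidable weakness, not evidence that bias will occur.

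Its size cannot be computed from the documents. The range of 6.6% to 20.3% rests entirely on assumed shifts of 0.1 to 0.3 SD. A fully algorithmic rule, fixed in advance and applied to every drive alike, would leave little of the concern. Visit-masked scoring is a worthwhile, inexpensive improvement; restricting the quarterly summaries is optional.

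**What to change.** **Section 6, Masking.** Replace the sentence with text to this effect:

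> Participants and trainers are not masked. Evaluation-drive files are given random codes that conceal the visit. Scan classification and hazard-detection scoring, and the checking of both, are done without knowledge of visit, using one written rule fixed before the first file is scored.

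The codes should be assigned automatically, or by a team member who neither scores nor checks data. The second researcher in section 10 checks all data, so holding the key would unmask that check. Dates and visit numbers should be removed from file names. The rule should state the tracking signal and the numeric criteria for an early scan, a large scan and a detected hazard.

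**Section 10, Outcomes monitoring (optional).** Until the 16th participant completes Visit 5, limit the quarterly summaries to enrolment, withdrawals, safety, tracker data loss and completeness of outcome data. Outcome values pooled across visits could be added, so that the team can still notice an outcome that is not behaving as expected. Safety stays in the review, as section 10 requires.

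**Cost.** File relabelling and protocol wording, plus a key holder if the codes are not assigned automatically. The documents give no staffing figures, so the low cost is a judgement. If the optional part is adopted, the team gives up an early view of the pre/post effect. Sample size, α and power do not change.
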